8.4. Other Safety Analyses

The analyses of non-laboratory safety test results including ECGs and vital signs will be based on GSK Core Data Standards, unless otherwise specified.

Table 6 provides an overview of the planned other safety analyses, with full details of data displays being presented in Appendix 9: List of Data Displays.

Table 6 Overview of Other Safety Analyses

Endpoint / Parameter/ Display Type	Absolute		
	Summary	Individual	
	T	F ^[1]	L
ECG			
ECG Findings	Y		
All ECG Values for Subjects with any Value of PCI			Y
ECG Values of PCI			Y
Abnormal ECG Findings			Y
Maximum QTc Values Post-Baseline Relative to Baseline by Category	Y		
Change from Baseline in ECG Values by Visit	Y		
Maximum Increase in QTc Values Post-Baseline Relative to Baseline by Category	Y		
Echocardiogram and Cardiac Monitoring ^[2]			
Cardiac Telemetry			Y
Vital Signs			
Change from Baseline in Vital Signs	Y	Y	
All Vital Signs for Subjects with any Value of PCI			Y

NOTES:

- T = Table, F = Figures, L = Listings, Y = Yes display generated, PCI = Potential Clinical Importance
- Summary = Represents Tables related to any summaries (i.e. descriptive statistics) of the observed raw data.
- Individual = Represents FL related to any displays of individual subject observed raw data.
- [1] Individual figures of absolute values are profile plots by subject identifiers.
- [2] Cardiac monitoring comments will be listed from the clinical database. Individual subject narratives will be provided separately by investigator.

9. PHARMACOKINETIC ANALYSES

9.1. Primary Pharmacokinetic Analyses

The analyses in this section will be based on the “Pharmacokinetic (PK)” population, unless otherwise specified. Data will be listed and summarized according to the GSK reporting standards, where applicable. [Table 7](#) provides an overview of the planned PK analyses, with full details of data displays being presented in Appendix 9: List of Data Displays.

Table 7 Overview of Planned Pharmacokinetic Analyses

Endpoints	Absolute			
	Summary		Individual	
	T	F	F	L
PK				
Total mAb	Y	Y	Y	Y
⁸⁹ Zr-GSK2398852	Y	Y	Y	Y

NOTES :

T = Table, F = Figure, L = Listing, Y = Yes display generated.

9.1.1. Endpoint / Variables

Drug Concentration Measures

Refer to [Appendix 4](#): Data Display Standards & Handling Conventions

Derived Pharmacokinetic Parameters

Pharmacokinetic parameters will be calculated by standard non-compartmental analysis according to current working practices and using the currently supported version of WinNonlin. All calculations of non-compartmental parameters will be based on actual sampling times. Pharmacokinetic parameters listed will be determined from the plasma concentration-time data of both GSK2398852 and ⁸⁹Zr-GSK2398852, as data permits.

Parameter	Parameter Description
C _{max}	Maximum observed concentration
T _{max}	Time of first observation of maximum concentration
AUC _t	Area under the concentration time course till last observation
T _{1/2}	Terminal phase half life
AUC _{inf}	Area under the concentration time course till time infinity

NOTES:

- Additional parameters may be included as required.

9.1.2. Population of Interest

The pharmacokinetic analyses will be based on the “Pharmacokinetic (PK)” population, unless otherwise specified.

9.1.3. Statistical Analyses / Methods

Details of the planned displays are provided in [Appendix 9: List of Data Displays](#) and will be based on GSK Data Standards and statistical principles.

Unless otherwise specified, endpoints / variables defined in Section [9.1.1](#) will be summarised using descriptive statistics, graphically presented (where appropriate) and listed. No formal statistical models will be fit as part of the PK analysis.

Plasma concentrations of Total mAb, which is the total of both ⁸⁹Zr-labelled and unlabelled mAb, will be analysed using non-compartmental methods. PK parameters will be summarised by TMD.

Plasma radioactive concentration - measured by scintillation counter, corrected by radioactivity decay and expressed in molar concentration of the mAb - will be analysed by non-compartmental methods. This radioactive concentration will reflect the total of both labelled-mAb and its metabolites. PK parameters will be summarised by TMD, with/without stratification by treatment period.

For each anatomical region defined in the heart, the PET scans will generate up to 3 values on tissue radioactivity concentration (SUV), and the plasma radio-PK values will function as a marker of plasma clearance. The mechanistic model will probe the combination of tissue SUV and radio-PK as compatible with contributions by a vascular component, a free distribution to interstitium and a component related to tracer bound to amyloid-SAP complexes. The extracted parameters will be summarised for each subject and each mass dose.

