## **5.2. Part A and Part B**

The study will be divided into two parts. Part A will complete up to 3 subjects who participate in up to two anti-SAP dosing sessions. The first two subjects in Part A will have up to three  $^{89}\text{Zr}$  PET scans, while the remaining subject will undergo up to two  $^{89}\text{Zr}$  PET scans.

Part B will complete up to three subjects who participate in only one anti-SAP dosing session. Subjects will undergo up to two  $^{89}\text{Zr}$  PET scans.

[figure not shown]
Part B will be triggered by the sponsor in consultation with the Principal Investigator. This will be based on data obtained in Part A, which includes but is not restricted to equivocal myocardial uptake of  $^{89}\text{Zr}$ -GSK2398852 in all subjects treated in Part A. This decision will also be contingent based on emerging data from the concurrent Phase 2 trial (Study Number 201464).

[figure not shown]
Should Part B not be triggered, then the study will conclude with Part A.

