### **5.13.2. Justification of serial PET scanning per Anti-SAP session**

The time course of the radiolabel mAb PK profile, and the temporal pattern of  $^{89}\text{Zr}$ -GSK2398852 uptake in the myocardium are the two key parameters guiding anti-SAP mAb TMD selection in this PET study.

A total of up to 3 serial  $^{89}\text{Zr}$ -GSK2398852 PET scanning procedures will be performed per dosing session. The scanning times will be predefined only for the first patient, but may be different for the following patients, guided by previous results.

In Part A, the first two subjects will have 3 PET scans per dosing session. The first two scans in these two subjects will be performed over approximately the first 24 hours after  $^{89}\text{Zr}$ -GSK2398852 administration. The third scan will be performed at a later time (timing to be determined from emerging data during the initial part of the study).

After the first two subjects have completed Part A, the subsequent subjects are planned to undergo only two PET scans, the timing of which will be determined by emerging data.

Up to 3 PET scans per dosing session in Part A are justified after administration of  $^{89}\text{Zr}$ -GSK2398852 because the timing of each of these three scanning procedures is a reflection of the predicted time-related whole body biodistribution of  $^{89}\text{Zr}$ -GSK2398852. That is, a later PET scan performed at approximately 72 hours after administration of  $^{89}\text{Zr}$ -GSK2398852 is more likely to detect myocardial tissue specific uptake compared to PET scans performed at earlier time points which are more likely to detect  $^{89}\text{Zr}$ -GSK2398852 within the blood pool of the cardiac chambers.

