19. Third ⁸⁹Zr PET-CT to be done in first two subjects who complete Part A, only. Subsequent subjects to undergo only two ⁸⁹Zr PET-CT scans.
20. From Day 6 onward, at investigator discretion, inpatient cardiac monitoring can be performed via remote cardiac telemetry device (e.g. BodyGuardian® device)
21. If logistically possible.

Table 11 Allowable Assessment/Visit Windows

	Day 3: End mAb Infusion	Day 3: 4 hours post end-mAb infusion	Day 20	Day 26
Window	+10 minutes	±10 minutes	±1 day	±2 days

Table 12 Unlabelled anti-SAP mAb PK Sampling (Dosing Sessions 1 and 2)

	Pre anti-SAP mAb infusion	Halfway through infusion	End of unlabelled anti-SAP mAb infusion	7 hours post end of anti-SAP mAb infusion	24 hours after end of infusion (Day 4)	48 hours after end of infusion (Day 5)	72 hours after end of infusion (Day 6)	96 hours after end of infusion (Day 7)
Anti-SAP mAb PK	X	X	X	X	X	X	X	X
Time window		±10 minutes	+10 minutes	±30 minutes	±1 hour	±2 hours	±2 hours	±2 hours

Note: Up to three additional samples may be collected and sampling times may be modified based on emerging data.

Table 13 ⁸⁹Zr-GSK2398852 Radio-PK Sampling (Dosing Sessions 1 and 2)

	Time after ⁸⁹ Zr-GSK2398852 infusion end						
	10 minutes	60 minutes	4 hours	7 hours	24 hours (Day 4)	48 hours (Day 5)	72 hours (Day 6)
⁸⁹ Zr-GSK2398852 radio-PK (for scintillation)	X	X	X	X	X	X	X
Time Window	± 5 minutes	± 10 minutes	± 1 hour	± 2 hours	± 4 hours	± 4 hours	± 4 hours

Note: Up to three additional samples may be collected and sampling times may be modified based on emerging data. Time windows are for guidance; non-adherence to these times will not constitute a protocol deviation.

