For the regions in the 4*5 scans focused over the heart, separate and average values will be generated for each of the Rols.

Total organ radioactivity amount in Regions of Interest (RoI)

- Heart
- Liver
- Spleen
- One lung
- Each kidney

Other organs may be included depending on features in the images.

Analysis of PET Data

The tissue SUV and plasma radio-PK values generated will constitute the primary information from the studies. Since plasma radio-PK will be dependent upon time after administration plus mass dose, it will be necessary to relate the tissue SUV to the instant and possibly also to the AUC of the plasma radio-PK.

It is expected that the tissue-to-plasma ratio of the mAb in the heart will be approximately 0.1-0.2 after equilibration between plasma and tissue interstitium. This is guided by an expected plasma

space plus interstitium relative space of 0.1-0.2. Within the blood pool of the heart chambers the ratio is expected to be 0.5 (hematocrit about 0.5).

We have placed a limit by which the tissue-to-plasma ratio in the cardiac muscle is indicative of entry to the interstitium and binding to amyloid-SAP complexes at 0.5 in balance between a sufficient increase as compared to passive distribution and avoidance of “spill-over” from cardiac blood pools.

More complex models of distribution between plasma and tissue may be explored.

Storage and potential further analyses of images

The primary PET and CT images in digital form will be anonymized and stored in an image repository under the control of GSK and may be used for further analyses.

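### SAP 9.1.3 promises vascular, free and bound parameters for each subject and mass dose without saying what is fixed or shared; 5 of 9 planned sessions give two SUVs per heart region, no display reports the parameters, and Table 4.5 tabulates plasma by heart region

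*SAP*

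**What the plan says.** SAP 9.1.3 notes that for each heart region "the PET scans will generate up to 3 values on tissue radioactivity concentration (SUV"), with plasma radio-PK as the marker of plasma clearance. A mechanistic model then examines the two together "as compatible with contributions by a vascular component, a free distribution to interstitium and a component related to tracer bound to amyloid-SAP complexes". On reporting it says: "The extracted parameters will be summarised for each subject and each mass dose". Earlier the same section says: "No formal statistical models will be fit as part of the PK analysis". It gives no equations, no fixed or shared terms and no rule for sessions with fewer than three scans.

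The number of scans differs by subject. The first two Part A subjects have three per session. For the third, protocol 5.2 says "while the remaining subject will undergo up to two" scans. Protocol 5.13.2 says "the subsequent subjects are planned to undergo only two PET scans", with timing left to emerging data. Footnote 19 of the schedule in SAP 12.2.1 agrees that the third scan is a "PET-CT to be done in first two subjects who complete Part A, only".

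The one figure that could serve as a constraint is in SAP 12.4.5: "It is expected that the tissue-to-plasma ratio of the mAb in the heart will be approximately 0.1-0.2 after equilibration between plasma and tissue interstitium". It is used there to support the 0.5 ratio limit and is not declared as a model input.

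Appendix 9 of the SAP names the model parameters in no table, figure or listing. Tables 4.3 and 4.4 and Listings 41 and 42 hold plasma PK parameters, which SAP 9.1.1 defines by non-compartmental analysis. Table 4.5 is a summary of plasma tracer concentration over time by anatomical region, and its shell PK_T1 has heart regions as rows.

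**The concern.** The bound term is the quantity that would separate binding to cardiac amyloid from passive uptake. It matters more because SAP 2.2 records that the PiB and labelled-water scans, meant to put uptake in context, were dropped. If the SUVs do not fix the bound term, its value depends on what the modeller chose to hold constant or share, and the SAP does not record that choice.

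The display problem is separate and simpler. Plasma concentration does not vary by heart region, so Table 4.5 cannot be produced meaningfully as titled. If tissue SUV was meant, the shell's mean, SD, median and confidence interval conflict with SAP 2.2, which rules out descriptive statistics for every PET imaging endpoint. Table 4.5 is due at both the interim and the final analysis.

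**Working it through.** **Count of sessions** (protocol 5.2 and 5.13.2; SAP 2.6)

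- Part A: 3 subjects × 2 sessions = 6. Part B: 3 × 1 = 3. Total 9, from the 6 subjects that the SAP states.
- Three scans: 2 subjects × 2 sessions = 4. This matches the SAP's maximum of 3 values per region.
- Two scans: third Part A subject 1 × 2, plus Part B 3 × 1, gives 5 of 9. Without Part B it is 2 of 6.

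**Unknowns against data, one region and one session fitted alone**

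- Three component weights against 2 SUVs: 3 − 2 = 1 too many.
- Three weights against 3 SUVs: 0 residual degrees of freedom. That is the best case, since any unknown rate constant adds to the count.
- Repeat frames do not help. Shell PD_L1 averages SUVpeak over the 20-minute scan.

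**What sharing could do.** PD_L1 has four myocardial regions (left ventricular wall and mid septum, each high and low). Two scans give 4 × 2 = 8 SUVs.

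- Nothing shared: 4 × 3 = 12 unknowns.
- Vascular shared: 1 + 4 + 4 = 9.
- Vascular and free shared: 1 + 1 + 4 = 6, fewer than 8.

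The last could work, but protocol 3.2.2 says the endothelium may be impaired where amyloid lies. Sharing across sessions is impossible in Part B (one session). In Part A, a bound term shared across sessions would assume away the displacement examined in protocol 10.3.4.

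**Illustration.** The exchange model, its rates and the 24 h and 72 h scan times are assumptions. The 15 h half-life is the protocol 5.13.1 figure for 80 mg; 30 h and 60 h are assumed.

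- Plasma: Cp = exp(−λt), with λ = ln 2/15 = 0.0462 per h.
- Tissue: v·Cp + F + B, where dF/dt = K1·Cp − (k2 + k3)F and dB/dt = k3·F.
- Truth: v = 0.05, K1/k2 = 0.1, k2 = 0.1 per h, k3 = 0.005 per h. Tissue/plasma ratios are 0.19 at 24 h and 0.49 at 72 h, with 55% of the 72 h signal bound.

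Two other solutions fit both values exactly:

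- No binding: v = 0.077, K1 = 0.00451, k2 = 0.04 per h. The ratio is v + K1·(exp((λ − k2)t) − 1)/(λ − k2). At 72 h this is 0.077 + 0.00451 × 0.564/0.00621 = 0.49. The passive space is 0.077 + 0.00451/0.04 = 0.077 + 0.113 = 0.19, inside the plan's 0.1–0.2.
- Instant exchange: passive ratio 0.17, so bound share = (0.49 − 0.17)/0.49 = 65%.

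Adding a 5 h scan, a no-binding model still fits all three values within 0.02%.

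Bound share at 72 h compatible with two scans, allowing v from 0 to 0.3 and K1/k2 from 0 to 0.4:

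| Assumed k3 (per h) | Scans | 15 h | 30 h | 60 h |
|---|---|---|---|---|
| 0.005 | 24 + 72 h | 0–65% | 0–42% | 0–33% |
| 0.05 | 24 + 72 h | about 40–95% | 22–86% | 13–79% |
| 0.005 | 5 + 72 h | 0–81% | | |

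Fixing a term settles the answer without making it right. With no true binding (15 h; washout 0.06, 0.1 and 0.2 per h), instant exchange reports 51%, 22% and 2% bound. A passive ratio fixed at 0.1 reports 69%, 57% and 44%; fixed at 0.2 it reports 38%, 14% and a negative value.

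**The case against.** The best defence is that the detail belongs elsewhere. SAP 12.4.4 leaves the PET variables to the imaging centre, the protocol sends image-analysis detail to an imaging manual not available here, and SAP 12.4.5 says more complex models may be explored. SAP 9.1.3 also speaks of probing what is compatible with three components, which is close to reporting a range. This stands in part: the model may be specified in another document, and citing that document would answer the point. But none of these passages specifies it, SAP 9.1.3 does not cite the manual for it, and protocol 10.3.5 says full details will be in the analysis plan. PK_T1 is also visibly an unedited template, so Table 4.5 is probably a labelling error. It still needs correcting.

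Four stronger readings are tempting and are not supported:

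- **Two scans can never show binding.** The ranges that include zero rest on one weak assumed rate, 0.005 per h. With k2 = 0.1 per h it gives 72 h ratios of 0.49, 0.25 and 0.21, all below the plan's 0.5. At 0.05 per h zero is excluded at all three half-lives. Scan times are also open, since protocol 5.13.2 leaves the later ones to emerging data. A ban on point estimates from two-scan sessions does not follow.
- **Keeping unknowns no more numerous than SUVs is a cure.** The three-scan example is saturated and still fits no binding.
- **The 0.5 ratio limit is a safe fallback.** The no-binding solution above gives a ratio of 0.67 at 96 h, inside the roughly 5-day scan window, so the limit is not shown to be unaffected. One assumed example does not show that it fails either.
- **The SAP contradicts itself on models.** A mechanistic model need not be a formal statistical model. This is a tension in wording only.

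**Conclusion.** The point holds as a gap in specification and an error in one display. The parameter count rests on the documents alone: 5 of 9 sessions at planned maxima, or 2 of 6 without Part B, cannot determine three components for one region and session, and the other four are at best saturated. These are planned maxima. Protocol 5.3.1 lets the number and timing of scans vary after the first subject, and protocol 5.11 allows a Part A subject to complete with one session.

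The size of the ambiguity is not a property of the plan. It ran from 0–65% to about 40–95% bound at a 15 h half-life when the assumed binding rate changed tenfold, and it moved again with scan times. What the illustration shows is that the constraint chosen can decide the answer, so it should be written down.

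The weight is low. The study tests no hypothesis, its size was set by feasibility, and the primary SUV listings do not change. The change is still worth making, because it is cheap and Table 4.5 cannot stand as written.

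**What to change.** 1. In SAP 9.1.3, state which terms are fixed or shared, across which regions or sessions, and from what source (for example the 0.1–0.2 space in 12.4.5 or the blood-pool SUVs in PD_L1), or cite the document that states this.
2. Where the SUVs and the stated constraints do not determine the bound term, whatever the number of scans, report the range compatible with the data under bounds set beforehand for vascular space, free space and washout. Say whether the range includes zero. Show any point estimate only beside that range, with its fixed or shared terms, as a sensitivity analysis.
3. Replace Table 4.5 with a listing of the extracted parameters by subject, total mass dose, session and region, showing the number of scans and the fixed or shared terms.

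Cost: SAP wording, model set-up, and one listing in place of one table. No new data are needed. The downside is that some bound terms will be reported as wide ranges.

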10. PHARMACODYNAMIC AND BIOMARKER ANALYSES

The analyses in this section will be based on the “Safety” population, unless otherwise specified. Data will be listed and summarized according to the GSK reporting standards, where applicable. [Table 8](#) provides an overview of the planned PD analyses, with full details of data displays being presented in Appendix 9: List of Data Displays.

Table 8 Overview of Planned Pharmacodynamic Analyses

Endpoints	Absolute			
	Summary		Individual	
	T	F	F	L
Cardiac biomarker				
Troponin T, NT-ProBNP				Y
Plasma SAP Concentration				Y

NOTES :

T = Table, F = Figure, L = Listing, Y = Yes display generated.

12. APPENDICES

12.1. Appendix 1: Protocol Deviation Management and Definitions for Per Protocol Population

12.1.1. Exclusions from Per Protocol Population

There is no per protocol population defined for this study.

12.2. Appendix 2: Schedule of Activities

12.2.1. Protocol Defined Schedule of Events

Table 9 Part A and Part B Overview

	Dosing Session 1	Dosing Session 2
Part A	X	X
Part B	X	

Table 10 Overview All Groups

	Screening ¹	Baseline ²	Dosing Sessions 1 and 2																		
			Day 1: pre- dose	Day 1	Day 2	Day 3: pre-dose mAb	Day 3: anti-SAP mAb dosing	Day 3: end of mAb infusion ¹⁸	Day 3: 4 hours post end mAb infusion ¹⁸	Day 4	Day 5	Day 6	Day 7	Day 8	Day 9	Day 10	Day 11	Day 11-18	Day 20 ¹⁸	Day 26 ^{16, 18}	
Inpatient stay at unit			-----X-----																		
Discharge from inpatient																	X				
Outpatient visit	X	X																		X	
Remote Contact for Safety Assessment																			X		
Informed consent	X																				
Medical history/risk factors/demographics	X																				
Inclusion/exclusion criteria	X																				
Safety Assessments																					
Physical examination ³	X		X			X		X			X			X			X				
Adverse event (AE)/ serious adverse event (SAE) Assessment			-----X-----																		
Concomitant Medications			-----X-----																		
12-lead electrocardiogram (ECG)	X ¹³		X ¹³		X	X		X	X	X	X	X	X	X	X	X	X		X ²¹	X	
Continuous Lead II Telemetry ²⁰			-----X-----																		

		Dosing Sessions 1 and 2																			
	Screening ¹	Baseline ²	Day 1: pre-dose	Day 1	Day 2	Day 3: pre-dose mAb	Day 3: anti-SAP mAb dosing	Day 3: end of mAb infusion ¹⁸	Day 3: 4 hours post end mAb infusion ¹⁸	Day 4	Day 5	Day 6	Day 7	Day 8	Day 9	Day 10	Day 11	Day 11-18	Day 20 ¹⁸	Day 26; ^{16, 18}	
Remote Continuous Cardiac Monitoring ⁴		X															X	X			
Vital signs	X ₁₃		X		X	X		X	X	X	X	X	X	X	X	X	X	X		X ₂₁	X
Screening Laboratory Assessments ⁵	X																				
Haem/clin chem/urinalysis	X		X			X					X		X				X				X
Troponin T/ N-terminal prohormone of brain natriuretic peptide (NT-ProBNP)	X		X		X	X				X	X	X	X	X	X	X					X
Pregnancy Test	X ₁₅		X ₁₅																		
Investigational medicinal product (IMP) Administration																					
Carboxy pyrrolidine hexanoyl pyrrolidine carboxylate (CPHPC) IV																					
CPHPC SC ¹²								X ₁₁		X	X	X	X	X	X	X	X				
Premedication (hydrocortisone/anti-histamine)						X															
Unlabelled anti-SAP mAb							X ₇														
⁸⁹ Zr-GSK2398852							X ₇														
Pharmacokinetics (PK)/SAP ⁹																					
Blood sampling for plasma SAP			X		X ₆																
Anti-SAP mAb PK ¹⁷							X	X	X	X	X	X	X								
⁸⁹ Zr-GSK2398852 radio-PK (for scintillation) ¹⁴							X	X	X	X	X	X									

		Dosing Sessions 1 and 2																			
	Screening ¹	Baseline ²	Day 1: pre-dose	Day 1	Day 2	Day 3: pre-dose mAb	Day 3: anti-SAP mAb dosing	Day 3: end of mAb infusion ¹⁸	Day 3: 4 hours post end mAb infusion ¹⁸	Day 4	Day 5	Day 6	Day 7	Day 8	Day 9	Day 10	Day 11	Day 11-18	Day 20 ¹⁸	Day 26 ^{16, 18}	
Imaging Procedures																					
Cardiac Magnetic Resonance Imaging (MRI) with contrast		X																			
Echocardiogram (ECHO)		X																			
Pittsburgh Compound B (PIB) Positron Emission Tomography (PET)		X																			
15-Oxygen labelled water (WAT PET)		X			X ₈																
⁸⁹ Zr-GSK2398852 PET / Computerised Tomography (CT)								X ₉	X ₉		X _{9, 19}										

Note: If anti-SAP mAb dosing is delayed by one day, then Day 2 assessments should be repeated, and all subsequent assessments should be delayed by one day.

Footnotes:

1. Screening to take place within 35 days of start of Anti-SAP treatment.
2. Baseline will be any time after eligibility confirmed and before Anti-SAP treatment starts. Procedures may be done on different days.
3. Full examination at screening only, brief examination at all other time-points.
4. Out-patient cardiac recording (see Protocol Section 3.4.1.3): Baseline for approximately 1 week, and from Day 11 for approximately 1 week after discharge.
5. See Other Screening Tests in Protocol Appendix 2
6. Requires rapid turnaround. See Protocol Section 5.5
7. See Protocol Section 5.6 for timing of administration of unlabelled anti-SAP mAb and ⁸⁹Zr-GSK2398852.
8. Dosing Session 2 only, if logistically feasible. Can be done any day/time prior to anti-SAP mAb.
9. Exact timing in relation to end of ⁸⁹Zr-GSK2398852 infusion will change based on emerging data. See Protocol Section 5.3.1
10. CPHPC IV infusion for a minimum of approximately 48 hours. To be stopped prior to mAb infusion.
11. First SC dose to be administered approximately 5 hours after end of IV CPHPC infusion.
12. Administered three times daily. See Protocol Section 7.1 and Section 7.2
13. In triplicate.
14. See Protocol Table 5
15. Female Subjects Only.
16. The last visit of the final study session will be considered the final follow-up visit. This may be conducted in-person, or by “virtual visit”.
17. See Protocol Table 4 for sampling times and windows.

18. See Protocol Table 3 for allowable time/visit windows.
19. Third ⁸⁹Zr PET-CT to be done in first two subjects who complete Part A, only. Subsequent subjects to undergo only two ⁸⁹Zr PET-CT scans.
20. From Day 6 onward, at investigator discretion, inpatient cardiac monitoring can be performed via remote cardiac telemetry device (e.g. BodyGuardian® device)
21. If logistically possible.

Table 11 Allowable Assessment/Visit Windows

	Day 3: End mAb Infusion	Day 3: 4 hours post end-mAb infusion	Day 20	Day 26
Window	+10 minutes	±10 minutes	±1 day	±2 days

Table 12 Unlabelled anti-SAP mAb PK Sampling (Dosing Sessions 1 and 2)

	Pre anti-SAP mAb infusion	Halfway through infusion	End of unlabelled anti-SAP mAb infusion	7 hours post end of anti-SAP mAb infusion	24 hours after end of infusion (Day 4)	48 hours after end of infusion (Day 5)	72 hours after end of infusion (Day 6)	96 hours after end of infusion (Day 7)
Anti-SAP mAb PK	X	X	X	X	X	X	X	X
Time window		±10 minutes	+10 minutes	±30 minutes	±1 hour	±2 hours	±2 hours	±2 hours

Note: Up to three additional samples may be collected and sampling times may be modified based on emerging data.

Table 13 ⁸⁹Zr-GSK2398852 Radio-PK Sampling (Dosing Sessions 1 and 2)

	Time after ⁸⁹ Zr-GSK2398852 infusion end						
	10 minutes	60 minutes	4 hours	7 hours	24 hours (Day 4)	48 hours (Day 5)	72 hours (Day 6)
⁸⁹ Zr-GSK2398852 radio-PK (for scintillation)	X	X	X	X	X	X	X
Time Window	± 5 minutes	± 10 minutes	± 1 hour	± 2 hours	± 4 hours	± 4 hours	± 4 hours

Note: Up to three additional samples may be collected and sampling times may be modified based on emerging data. Time windows are for guidance; non-adherence to these times will not constitute a protocol deviation.

